This is a randomized, blinded, placebo-controlled pilot study. A stratified block randomization procedure will be used to ensure that each group has an equal number of men, and an equal number of women. Blocks will be made in groups of 4 for each sex. Given that the majority of cardiac surgery patients are male, each group is not expected to be made of an equal number of men and women. The randomization procedure will be done with preprepared numbered envelopes. Separate piles of envelopes will be kept to randomize each sex separately. Each envelope will contain the group assignment of either "Ketamine" or "Placebo". Group assignment papers will be inserted in the envelopes in a random order. A list of the group assignment in each numbered envelope will be kept separate from study materials while the study is being carried out. This measure will help ensure that the research coordinator will be blinded during data collection. A separate list will be made by a coinvestigator not involved in the data analysis denoting which envelopes corresponded to "Group A" and "Group B" to allow for the primary investigator to be blinded during data analysis, and for the study coordinator to ensure stratified randomization has distributed an equal number of patients of each sex in each group by the end of the study.

Either the cardiac surgeon, the cardiac anesthetist or a nurse involved in the patients' care will ask the patient if the research coordinator can approach the patient to discuss

inclusion in the study. The research coordinator will then discuss risks and benefits of being included in the study and obtain consent.

On the day of the procedure the research coordinator will randomly select a numbered envelope for the appropriate sex, and hand this to one of the two other co-investigators prior to surgery. One of the two co-investigators will prepare the study drug.

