The intervention group will receive Ketamine, while the placebo group will have an identical syringe of normal saline prepared. The placebo will be prepared to blind the cardiac anesthetist caring for the patient. This blinding is important as the quantity of narcotic administered during the surgery is at the anesthetist's discretion, and knowing whether or not a co-analgesic is being administered may affect the quantity of narcotic administered. The quantity of narcotic administered could be considered a co-intervention of the primary outcome, so we are taking all precautions to ensure that the amount of narcotic administered is not influenced by the anesthesiologist's knowledge of the study drug.

The cardiac anesthesiologist will receive the medication in the operating room, delivering a bolus prior to skin incision and administering the medication at a rate determined by the patient's weight. The dose of medication administered should not have any hemodynamic effects, and so unblinding of the cardiac anesthetist should not be necessary. If, for whatever reason unblinding should become necessary, the co-investigator who prepared the medication will make the primary anesthetist aware of the contents of the study drug.

Upon transfer to the intensive care unit, nurses and intensive care physicians will be made aware that the patient is involved in the study. The research coordinator will have documented the volume of study drug administered in the anesthetic record at the end of the

case. If the treatment allocation needs to be known by the intensive care team, they will be able to contact the primary investigator to be immediately unblinded.

Patients will be asked if they would allow the research coordinator to call them at 3 and 6 months after surgery to ask if any pain is present at the site of incision, followed by ten yes or no questions about the pain, and what medications they may be taking for pain, if the pain is still present. These questions can be found in the attached questionnaire.¹⁴

Study Population

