On follow-up phone call at 3 and 6 months patients will be asked whether or not they have persistent pain at the site of the sternotomy. Whether or not persistent pain is present will be noted, along with any medications that they may be taking for the pain. If persistent pain is present, they will be asked ten yes or no descriptive questions about the pain concerning to determine if it is neuropathic in origin.¹⁴ The answer to each question, as well as the overall score will be noted.

Confounders

Possible baseline confounders will be tracked to look for differential distribution between intervention groups. These will include age, sex, body mass index, left internal mammary harvesting. We will stratify our randomization by sex to ensure sexes are balanced in the 2 groups, as sex has been shown to be one of the main confounders for postoperative pain. With a relatively small sample size of 80 patients, a differential distribution of confounders between groups is possible, and an adjustment will be done in our analysis for any factor that is differentially distributed. Injuries during cardiac surgery such as rib fracture and dislocation, or fractured sternum may contribute to postoperative pain as well. Unfortunately, these variables often go undetected and cannot be adequately tracked. We will therefore rely on randomization to ensure equal distribution in both groups.

Analysis Plan

While nearly complete compliance is expected with the therapy, an intention-to-treat analysis will be performed in case any unforeseen issues with compliance arise during the study. Continuous data such as postoperative opioid dose, intensive care unit and hospital length of stay, and time to mobilization and ambulation will be evaluated using the t test if it is determined that the means are normally distributed, or the Wilcoxon Rank Sum test if the means are not normally distributed. Ordinal data such as visual analog scale scores and binary data such as need for additional analgesics and the presence or absence of PONV will be evaluated by a Chi-Square test. If confounding is suspected due to baseline differences in the variables noted above, we will perform a propensity score depending on the variable(s) and the size of the difference. As a secondary analysis, data will be analyzed in subgroups by sex to look for any potential difference in response.

Sample Size & Power Analysis

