Using the data in the trial evaluating S(+)-Ketamine, an estimate of 125mg of oxycodone over the 48 hours post cardiac surgery was used as a baseline.¹ In this same study, both the intervention and controls groups had standard deviation of oxycodone of 45mg. To detect a decrease in opioid requirements of 25% with a power of 80% and a two-sided alpha of 0.05, a total of 68 patients would be required in the trial, with 34 in each group. For a power of 90%, a total of 90 patients would be required in the trial with 45 patients in each arm. The Jewish General Hospital, a McGill University teaching hospital, performs approximately 600 cardiac surgeries per year, with approximately 350 CABG surgeries via sternotomy. The goal will be to

enroll 80 patients. With the nature of this study and the need for hospitalization post-cardiac surgery, there should be minimal, if any, drop-outs or loss to follow-up, and therefore the sample size of 80 patients should allow for a power of over 80%.

Strengths & Limitations

Strengths of the study include the ability to randomize, and the ability to blind the patients, nurses, anesthesiologists and pain evaluators. This study will be performed at a single center, which allows for easier standardization of therapy, at the same time limiting generalizability of the findings. The primary outcome, opioid use, is easily measurable.

Limitations will include the inter-individual variability in both patient thresholds for analgesia request, and nurse thresholds to administer analgesia. Injury during cardiac surgery may contribute to pain (rib fracture or dislocation), and will not be able to be accurately measured.

Timetable

The Jewish General Hospital currently performs approximately 350 CABG surgeries per year, which is approximately 30 per month. Once ethics approval is obtained, and organizational logistics are arranged, the goal would be to recruit 80 patients over the span of four months. Another 2 to 3 months will likely be required for full data analysis and manuscript preparation.

References

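### The Timetable leaves no time for the 3- and 6-month pain calls: it finishes at month 6 to 7, but the last 6-month call falls at month 10

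*Combined protocol and SAP*

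**What the plan says.** Study Design sets up the late follow-up: "Patients will be asked if they would allow the research coordinator to call them at 3 and 6 months after surgery". The Outcomes section makes it a data item: "On follow-up phone call at 3 and 6 months patients will be asked whether or not they have persistent pain". Those who report pain also answer ten yes/no questions meant to identify a neuropathic origin, and pain medication is recorded.

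The Timetable gives two durations. For recruitment, "the goal would be to recruit 80 patients over the span of four months". For everything after that, "Another 2 to 3 months will likely be required for full data analysis and manuscript preparation". It contains no follow-up period. No section describes a first report of in-hospital results with a later report of the telephone data.

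On blinding, Study Design says: "A list of the group assignment in each numbered envelope will be kept separate from study materials while the study is being carried out". The stated purpose is to keep the research coordinator blinded during data collection. A second list, using Group A and Group B labels, is made "to allow for the primary investigator to be blinded during data analysis" and is also to be used by the coordinator to check balance by sex. No date or event is given for breaking the code.

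**The concern.** The outcome schedule and the calendar do not fit together. The calls are timed from each patient's surgery, so the last one falls six months after the last operation. The Timetable allows two to three months between the end of recruitment and a finished paper.

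Two things are at stake.

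- **Completeness.** Background names the effect of ketamine on chronic post-sternotomy pain as unstudied, and the two calls are the only data in the trial that address it. Retention of patients is also one of the feasibility questions in Specific Aim & Hypothesis, and an analysis that closes before the last call cannot describe retention to 6 months. The expectation of little loss to follow-up in Sample Size & Power Analysis rests on patients being in hospital, which does not cover calls made months later.
- **Bias.** Persistent pain is a patient-reported yes/no answer taken by the coordinator, so it is open to influence if either party knows the allocation. A paper comparing ketamine with placebo needs the code. If it is written on the stated calendar, the code might be opened while calls are still outstanding.

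**Working it through.** **Inputs.** Recruitment: 80 patients in 4 months (Timetable). Analysis and paper: a further 2 to 3 months (Timetable). Calls: 3 and 6 months after surgery (Study Design, Outcomes). Case volume: "approximately 350 CABG surgeries per year, which is approximately 30 per month" (Timetable). Assumptions: accrual is even, and surgery takes place at enrolment. Any wait between enrolment and surgery only makes the calls later.

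**The plan's own finish date.** 4 + 2 = month 6; 4 + 3 = month 7.

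**Last calls.** 3-month: 4 + 3 = month 7. 6-month: 4 + 6 = month 10.

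**Calls due by month t.** For a call L months after surgery and even accrual over A months, the share due is min(1, max(0, (t − L)/A)). With A = 4 and 80 patients:

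| Month t | 3-month calls due | 6-month calls due |
|---|---|---|
| 4 (recruitment ends) | (4 − 3)/4 = 25%, 20 of 80 | 0 of 80 |
| 6 (early finish) | (6 − 3)/4 = 75%, 60 of 80 | (6 − 6)/4 = 0%, 0 of 80 |
| 7 (late finish) | 100%, 80 of 80 | (7 − 6)/4 = 25%, 20 of 80 |
| 8 | 80 of 80 | (8 − 6)/4 = 50%, 40 of 80 |
| 10 | 80 of 80 | 100%, 80 of 80 |

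These counts favour the plan, because a call made on the day the paper is finished could not be in it.

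**If accrual is front-loaded.** Only patients operated on in month 1 are due by month 7. Even if every one of the roughly 30 monthly cases were enrolled, that is 30/80 = 37.5%.

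**If accrual takes longer.** The planned finish is at A + 2 to A + 3 and the last 6-month call at A + 6. The gap is (A + 6) − (A + 3) = 3 months to (A + 6) − (A + 2) = 4 months, for any A. The share of 6-month calls due at the finish does change. At A = 5 it is 1/5 to 2/5 (20% to 40%), at A = 6 it is 2/6 to 3/6 (33% to 50%), and at A = 8 it is 4/8 to 5/8 (50% to 63%).

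**A calendar that holds the follow-up.** Last call at month 10, plus the plan's own 2 to 3 months, gives completion at months 12 to 13.

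**Sample size.** This does not depend on the calendar, and it reproduces. The difference is 0.25 × 125 = 31.25 mg with SD 45 mg. A two-sample t-test calculation gives 33.5, so 34 per arm (68) for 80% power, and 44.6, so 45 per arm (90) for 90%. Power at 40 per arm is 86.6%.

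**The case against.** The strongest reply is that the Timetable is hedged planning text, expressed as a goal and a likelihood, while the calls are prescribed in two other sections and nowhere cancelled. A reader might infer that the 6-month outcome would be lost. The documents do not support that, since the calls could continue after month 7 and be reported separately. What remains is that the Timetable speaks of the full analysis, provides for no second report, and leaves a gap of 3 to 4 months at any accrual length. The hedging softens the durations but does not supply the missing follow-up period.

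A reader might also infer that allocation will be revealed to the caller. That goes too far. Study Design keeps the allocation list apart during the study, and the calls can fairly be counted as part of it; the analysis is to run under A/B labels. Unblinding is a risk and not a stated event. The risk stands because nothing says that the study lasts, for this purpose, until the last call. The coordinator also has a use for the A/B list, so decoding the letters in a paper could identify individual patients' arms to the caller.

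Nor should the importance be overstated. The title refers to postoperative pain, the specific aim and hypothesis concern opioid consumption, and the calls need the patient's agreement. Chronic pain is a secondary matter here, supported by the Background rationale.

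Finally, the statement that most 6-month data would be missing belongs to the planned four-month recruitment. With slower accrual the share due at the finish rises and can pass one half, although the last call still comes after the finish.

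**Conclusion.** The point stands as an inconsistency between the calendar and a stated secondary outcome. On the plan's own durations the finish is month 6 to 7 and the last 6-month call is at month 10. Assuming even accrual over four months, 75% to 100% of 6-month calls are not yet due at the finish, and a quarter of 3-month calls are not due if the finish is at month 6. The gap of 3 to 4 months does not depend on the accrual assumption.

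If the Timetable is followed, the full analysis would lack most 6-month pain data, and later calls might be made by a coordinator, or answered by patients, who know the allocation. The 48-hour primary outcome, the randomisation and the sample size are not touched. It should be corrected, because the repair is simple and these calls are the trial's only source of information on chronic pain.

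**What to change.** Add the follow-up period to the Timetable. Set the final data lock and the code-break after the last 6-month call, about month 10 at the planned accrual, with analysis and paper complete at about months 12 to 13. Define the date by that call and not by a calendar month, so that it moves with recruitment.

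If in-hospital results are wanted earlier, prespecify that analysis, run it under the Group A/B labels already provided for, and keep the code closed to the coordinator and patients until the last 6-month call. State this in Study Design beside the existing text on the allocation list.

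The cost is some wording and a later finish date: about six months later for the complete report (months 12 to 13 instead of 6 to 7). No extra patients, calls or staff are needed.
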